The Thrombosis Research Group has an infrastructure of experienced leadership, with trained personnel in a multidisciplinary academic team (research pharmacists, cardiology fellows, research nurses, research coordinators, biostatisticians, administrators, and medical informatics specialists). Data storage and computing resources, as well as a network of regional, national, and international collaborating investigators, facilitate our execution of ongoing research projects and our planning of future research projects. The Thrombosis Research Group has studied all aspects of VTE, including epidemiology, diagnosis, treatment, and prevention. According to www.pubmed.gov, the group has authored more than 100 Original Reports since 2010.

Drs. [name] and [name] have extensive experience leading randomized controlled trials focused on prevention and treatment of thromboembolic disease. Examples of major Thrombosis Research Group-lead trials in this area include the 2500-patient multicenter Electronic Alert Trial (40), the 2500-patient multicenter Physician Alert Trial (41), the 2500-patient Discharge Alert Trial (42), and the 85-patient multicenter eTRIS trial (35).

Vascular Medicine at BWH is a regional Center of Excellence for VTE care. An EPIC Electronic Health Record query of the outpatient clinic volume of the five Vascular Medicine faculty providers and the 4 full-time Vascular Medicine fellows

demonstrated a provoked VTE volume of approximately 1500 new and follow-up patients.

Table 7. EPIC query estimate of new and follow-up provoked VTE patient volume in 2018.

Provider	Provoked VTE Volume (patients/year)
[name]	300
[name]	400
[name]	400
[name]	100
[name]	100
4 Full-Time Vascular Medicine Fellows	200
TOTAL	1500

Since running this EPIC analysis, we have also added two additional full-time Vascular Medicine faculty, [name] and [name]. Both specialize in the care of patients with VTE and see frequent referrals for determination of optimal duration of anticoagulation and long-term secondary prevention of recurrent events. Furthermore, we will recruit from our inpatient cardiovascular medicine consult service and cardiovascular medicine ward service which receive a high volume of provoked VTE referrals. Accordingly, we anticipate having the ability to draw on these additional sources of provoked VTE patients for at least another 100 provoked VTE patients per year.

Even without the added VTE patient volumes of [name] and [name], we calculate 1600 new and follow-up provoked VTE patients who present for outpatient visits at BWH per year and we conservatively estimate that 25% will fail to meet all the inclusion criteria or will meet at least one exclusion criterion. Therefore, an estimated 1200 patients will be eligible for enrollment in the trial in the first year.

We will also have our research nurse run reports from EPIC to identify other patients in our non-Vascular Medicine cardiology practices that will be eligible but may not be scheduled to see us. We will also aggressively communicate the launch of the study to our non-Vascular Medicine cardiology colleagues. Furthermore, we will recruit from our inpatient cardiovascular medicine consult service and cardiovascular medicine ward service which receive a high volume of provoked VTE. Accordingly, we anticipate having the ability to draw on these additional sources of provoked VTE patients for at least another 100 provoked VTE patients per year.

As the trial will enroll over 20 months, we estimate that we will be able to draw from 1200 patients in the first year and 800 patients in the 8 months that comprise the second year of enrollment. This will yield 2000 patients from which to enroll 600 subjects for the trial.

Based on our prior clinical trial experience at the BWH Thrombosis Research Group, we conservatively estimate that 50% of the patients who are screened and found to be eligible for the trial will consent to participate. Therefore, an estimated 1000 eligible patients would be willing to provide informed consent to participate in the HI-PRO trial. Accordingly, enrollment of the planned 600-patient study population should be feasible and efficiently accomplished at BWH.

Additionally, the BWH Thrombosis Research Group has the infrastructure to operationalize this enrollment plan. The Thrombosis Research Group has two full-time dedicated research assistants, a research intern, a research nurse, three faculty physicians, a full-time advanced Vascular Medicine fellow, and a number of general Cardiovascular Medicine fellows who participate in our research studies. We have coordinated our ongoing research projects to accommodate the percent efforts required by our research staff and physician team members to maximize our success at enrollment for this trial. Accordingly, we have adequate staffing and physician support to add to the research personnel for this trial, identify eligible patients, and maintain our enrollment on track. We also have an adequate reserve in staffing and flexibility to augment our effort should enrollment require it.

TRG led the patient recruitment effort for the Cardiovascular Inflammation Reduction Trial (CIRT), a randomized, double-blind trial of low-dose methotrexate in 4786 patients with previous myocardial infarction or multivessel coronary disease who additionally had either type 2 diabetes or the metabolic syndrome (39). CIRT was a landmark study which involved a novel application of a challenging anti-inflammatory drug, serial laboratory evaluations, and a high number of follow-up phone calls and in-person office visits, which required patients to travel from as far as California to Boston. Despite these challenges, TRG made BWH the overall top enrolling site in the CIRT trial.

We anticipate rapid enrollment in the HI-PRO trial. First, all the patients in the study will be familiar with anticoagulation and many will have received apixaban. Second, there are no study-mandated laboratory tests or office visits. Third, many patients with provoked VTE are reluctant to discontinue anticoagulation after the acute treatment phase because of the fear of recurrent events. We anticipate that many patients with provoked VTE will be highly interested in participating in a clinical trial of extended secondary prevention thromboprophylaxis, especially with the favorable safety and efficacy profile of low-intensity apixaban. It is quite possible that greater than 50% of eligible patients will want to participate and provide informed consent. In such a scenario, we would expect to enroll more quickly.

Potential Risks and Benefits

Potential benefits to the subject

The potential benefit of treatment with low-dose apixaban in patients with provoked VTE is secondary prevention of VTE, including fatal PE.

Potential Benefits to Society

The major potential benefit to society of the proposed trial of apixaban for secondary prevention of VTE in patients with provoked VTE is that if successful, the study will provide the foundation for a new indication for extended-duration anticoagulation for VTE prevention. The data acquired from this randomized, placebo-controlled trial will establish the safety and efficacy of low-dose apixaban versus placebo for extended prevention of recurrence after provoked VTE in patients with at least one persistent provoking factor. The study will draw widespread interest for apixaban in the extended prevention of recurrence after provoked VTE and will most certainly be of interest to high-impact peer-reviewed journals and to a broad spectrum of clinicians who will be better able to care for their VTE patients using these data.

Potential Risks to the Subject

The foreseeable risk of apixaban for secondary prevention of VTE in patients with provoked VTE is major bleeding.

Risks of Research Procedures Performed on Subjects

The risk of research procedures includes psychological discomfort from participating in a clinical trial (less likely) and loss of confidentiality of medical records or economic data (rare).

Women of childbearing potential (able to get pregnant) must have a negative pregnancy test before being considered for the study. It is not known how apixaban could affect an unborn child. Women of childbearing potential must use an effective method of birth control while participating in this research, as directed by their physician.

Anticipated Risks of Drug

Adverse reactions occurring in $\geq 1\%$ of patients treated for DVT and PE in the AMPLIFY study (source table 6 USPI)

- Epistaxis
- Contusion
- Hematuria
- Menorrhagia
- Hematoma
- Hemoptysis
- Rectal hemorrhage
- Gingival bleeding

Less common adverse reactions occurring in Eliquis-treated patients in AMPLIFY or AMPLIFY-EXT studies occurring with a frequency of $\geq 0.1\%$ to $< 1\%$:

- Blood and lymphatic system disorders: hemorrhagic anemia
- Gastrointestinal disorders: hematochezia, hemorrhoidal hemorrhage, gastrointestinal hemorrhage, hematemesis, melena, anal hemorrhage
- Injury, poisoning, and procedural complications: wound hemorrhage, postprocedural hemorrhage, traumatic hematoma, periorbital hematoma
- Musculoskeletal and connective tissue disorders: muscle hemorrhage
- Reproductive system and breast disorders: vaginal hemorrhage, metrorrhagia, menometrorrhagia, genital hemorrhage
- Vascular disorders: hemorrhage
- Skin and subcutaneous tissue disorders: ecchymosis, skin hemorrhage, petechiae
- Eye disorders: conjunctival hemorrhage, retinal hemorrhage, eye hemorrhage
- Investigations: blood urine present, occult blood positive, occult blood, red blood cells urine positive
- General disorders and administration-site conditions: injection-site hematoma, vessel puncture-site hematoma

Additional information about the risks of apixaban can be found in the Apixaban Med Guide (see Appendix).

Protection of Subjects against the Risks of Research Procedures

Before Study Enrollment

A rigorous screening process will be utilized to ensure that subjects with an increased risk of harm due to enrollment in the study are excluded from the study. This will include performing a detailed history and physical examination (to ensure that enrolled subjects truly fulfill all eligibility criteria) and carefully reviewing the results of laboratory testing (in particular, hematocrit, platelet count, INR, and serum creatinine).

During Follow-Up

Changes in health status during the 12-month follow-up period will be evaluated by the patient's primary physician, and other routine providers. All subjects enrolled will also have ongoing medical care with a dedicated Vascular Medicine provider. As apixaban is an FDA-approved drug commonly used for thromboprophylaxis and does not require routine follow-up clinical or laboratory monitoring for toxicity, the study will not mandate any follow-up visits or procedures other than those required for the patient's routine care.

Protection against Loss of Confidentiality

Subject confidentiality will be protected by maintaining all paper records in locked file cabinets in locked offices and all electronic records in password-protected computer files. All study data will be de-identified for storage in the electronic data repository. In addition, any identifying information will be removed from images or other data used in publication or presentations. All database information will be stored on computer systems that are located behind an electronic firewall, which will only permit access to certified study personnel. Access to study data files will be password-protected.

Use of Information and Publication

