Specific Aim #1: To compare the 12-month rate of recurrent symptomatic VTE in patients with provoked VTE and at least one persistent provoking factor who are randomized to either apixaban (2.5 mg orally twice daily) as monotherapy or placebo after completing at least 3 months of therapeutic anticoagulation and who have a low risk of bleeding.

Hypothesis #1: Compared with placebo, oral apixaban (2.5 mg twice daily) will reduce the 12-month rate of symptomatic VTE in patients with provoked VTE and at least one persistent provoking factor who have completed at least 3 months of therapeutic anticoagulation and who have a low risk of bleeding.

Specific Aim #2: To compare the 12-month rate of ISTH major bleeding in patients with provoked VTE and at least one persistent provoking factor who are randomized to either apixaban (2.5 mg orally twice daily) as monotherapy or placebo after completing at least 3 months of therapeutic anticoagulation and who have a low risk of bleeding.

Hypothesis #2: Compared with placebo, oral apixaban (2.5 mg twice daily) will be associated with a similar rate of ISTH major bleeding at 12 months in patients with provoked VTE and at least one persistent provoking factor who are randomized to either apixaban (2.5 mg orally twice daily) as monotherapy or placebo after completing at least 3 months of therapeutic anticoagulation and who have a low risk of bleeding.

Introduction and Background

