- B. If the study is terminated or suspended, prompt notification will be provided to all parties of the study.
- C. Patient enrollment may be paused or terminated early if the DSMB determines that the potential benefits of continuing the trial are unlikely to outweigh the risks. For example, if the probability of achieving the target primary endpoints falls below a certain threshold, the trial will be stopped or paused for re-evaluation.

2. Safety Stopping Rules

The study will be terminated by the DSMB and principal investigator at any point if the following stopping criterion is met:

- a. An excess of morbidity or mortality is observed in patients receiving apixaban.
- b. When 3 of the subjects receiving apixaban experience an unprovoked intracranial hemorrhage, confirmed by independent adjudication and did not have a protocol violation such that he/she cannot be considered as representative of the intended patient population.
- c. When 3 of the subjects receiving apixaban experience an unprovoked major bleed (including fatal hemorrhagic events) and did not have a protocol violation such that he/she cannot be considered as representative of the intended patient population.

3. Stopping Rules for Futility

The study will be terminated by the DSMB and principal investigator if any of the following stopping criteria is met:

- a. Fewer than 36 events are observed in the placebo group at the time of the 300th patient interim statistical analysis
- b. Enrollment progress has been limited such that the study does not have a reasonable chance of randomizing 600 patients even after efforts to remediate recruitment

Protocol Violations

The study staff will rapidly and firmly address any protocol violations with the DSMB. If a protocol violation is detected or suspected, the investigator(s) will first be asked to provide a written explanation. After reviewing the available information, the study staff will categorize protocol violations as either major (eligibility or

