Table. 8 Harvard Catalyst Biostatistics Program Consultant Sample Size Calculation Using Lower Limit of 95% Confidence Interval of Our Observational Cohort Estimate (performed by [name] using STATA).

Anticipated Event Rate = 8.2%

. power twoproportions .082 .0205, test(chi2) n(558)
 
Estimated power for a two-sample proportions test
 
Pearson's chi-squared test
 
Ho: p2 = p1 versus Ha: p2 != p1
 
Study parameters:
 
 alpha = 0.0500
 
 N = 558
 
 N per group = 279
 
 p1 = 0.0820
 
 p2 = 0.0205
 
Estimated power: power = 0.9111
 
Required N = 279 per group

Using this more conservative sample size calculation, we would aim to enroll 300 patients in each arm for a total trial population of 600.

Statistical Analysis Plan

For this study, we will calculate:

- 1) the 12-month frequency of major and clinically relevant non-major bleeding
- 2) the 12-month frequency of symptomatic recurrent VTE

The primary efficacy objective of this trial is to determine whether apixaban 2.5 mg twice daily is superior to placebo for the primary endpoint of symptomatic, recurrent VTE after 12 months of extended therapy. The analysis will include descriptive statistics of event rates and 95% CI, and risk difference and 95% CI. The Mantel-Haenszel statistic will be used to test this hypothesis formally. Superiority over placebo will be claimed for a dose if the Hochberg adjusted p-value is ≤ 0.05 and the RR is < 1 . The analysis will be supported by Kaplan-Meier curves. The primary efficacy outcome analysis will be intention-to-treat. We will also perform an on-treatment analysis.

The primary safety objective will be to determine whether apixaban 2.5 mg twice daily results in a statistically significant difference in major bleeding at 12 months (during the treatment period) compared with placebo. Analysis of incidence of these endpoints will be based on the safety analysis set. The analysis will include descriptive statistics of event rates and 95% CI, and risk difference and 95% CI. Hypotheses will be tested using Mantel-Haenszel statistic. The analysis will be supported by Kaplan-Meier curves of the time to first adjudicated major bleeding event. All bleeding analyses will be conducted on the safety dataset.

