Patients who have experienced at least one persistent provoking factor following an initial provoked venous thromboembolism (VTE) are suspected to be at an increased risk of recurrence. However, it is still unclear whether extended-duration anticoagulation is beneficial for such patients. The HI-PRO randomized controlled trial conducted at Brigham and Women's Hospital (BWH) has been designed to investigate the safety and efficacy of extended-duration low-dose apixaban 2.5 mg twice daily for preventing recurrence in high-risk patients after initial provoked VTE.

2. Specific Aims

In this section, we provide an overview of the trial's specific aims. Based on the emerging evidence that provoked VTE patients may require extended-duration anticoagulation for secondary prevention, the apixaban 2.5 mg twice daily dose could be a critical addition to our armamentarium in those at high risk for recurrence at the transition of care from the acute to the chronic treatment phase. However, this hypothesis needs to be tested in a randomized clinical trial. We propose a single-center (BWH), randomized placebo-controlled trial conducted at to evaluate the impact of low-dose apixaban (2.5 mg twice daily) in a study population exclusively comprised of provoked VTE patients with at least one persistent provoking factor. We have the following study aims:

Specific Aim #1: To compare the 12-month recurrent symptomatic VTE in patients with provoked VTE and at least one enduring factor who are randomized to either apixaban (2.5 mg orally twice daily) as monotherapy or placebo after completing at least 3 months of therapeutic anticoagulation and who have a low risk of bleeding.

Specific Aim #2: To compare the 12-month ISTH major bleeding in patients with provoked VTE and at least one enduring factor who are randomized to either apixaban (2.5 mg orally twice daily) as monotherapy or placebo after completing at least 3 months of therapeutic anticoagulation and who have a low risk of bleeding.

3. Definitions

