6.4 Survival Analysis

6.4.1 Principal Analysis

We first provide analysis without adjustment of baseline demographics. For both the primary and secondary efficacy outcomes and principal and secondary safety outcomes, we use the Kaplan-Meier curve to estimate the survival functions of each group. If there is a presence of competing risks, cumulative incidence functions (CIFs) will be used to estimate the survival function⁷. The two-side log-rank test is used to measure if the apixaban 2.5 mg twice a day has a better survival chance than placebo (i.e., better chance of meeting the primary outcome). If there is a presence of competing risk, the log-rank based on cause-specific hazards⁸ will be used. The corresponding hazard ratio of treatment effect and its confidence interval will be reported.

While our analysis is based on randomization, we also provide confirmatory analyses with the adjustment of baseline demographics and clinical comorbidities since it may capture any potential variations to make the statistical analysis more powerful. We use Cox regression to assess both the primary and secondary efficacy outcomes, while with adjustment of baseline demographics and clinical comorbidities. No interaction effects will be added. If there are competing risks, a cause-specific hazard model⁷ will be used. The hazard ratio for being treatment with the apixaban 2.5 mg twice a day will be used to test the treatment effect. The hazard ratio of other baseline demographics will be reported as supplementary information.

If the trial has a good randomization, we expect that the hazard ratio of treatment in analysis with the adjustment of baseline demographics and its p-value implies the same conclusion as in analysis without adjustment of baseline demographics. However, if they are not consistent in

clinical interpretation, i.e., a) the interpretation directions are different; b) p-values indicate different conclusion of significance, we will use the hazard ratio of treatment in analysis with the adjustment of baseline demographics as the main results to report, and the results of unadjusted one is treated as supplementary materials.

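### Hypothesis #2 predicts similar major bleeding, but the only formal test is of a difference, with low power and no rule for judging similarity

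*Combined protocol and SAP*

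**What the plan says.** In the protocol's Specific Aims, Aim #2 is to compare 12-month major bleeding between the arms. Hypothesis #2 goes further and predicts that apixaban "will be associated with a similar rate of ISTH major bleeding at 12 months". No margin accompanies it.

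Under Statistical Methods, the protocol's Statistical Analysis Plan sets the primary safety objective as finding whether apixaban "results in a statistically significant difference in major bleeding at 12 months (during the treatment period) compared with placebo". It adds: "Hypotheses will be tested using Mantel-Haenszel statistic", two-sided at 0.05. It also plans estimates: "The analysis will include descriptive statistics of event rates and 95% CI, and risk difference and 95% CI".

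The separate SAP restates Aim #2 as "To compare the 12-month ISTH major bleeding in patients with provoked VTE and at least one enduring factor" and does not repeat the similarity hypothesis. Section 6.4.1 applies one sentence to efficacy and safety outcomes alike: "The two-side log-rank test is used to measure if the apixaban 2.5 mg twice a day has a better survival chance than placebo". The table in section 6.2.1 lists events, cumulative incidence, hazard ratio and 95% confidence interval for major bleeding in every analysis set, and a p-value only in the safety set. Section 6.1 says the power calculation addresses efficacy outcomes.

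The Protocol Summary gives the trial's purpose as establishing safety as well as efficacy. The protocol's Safety Stopping Rules include a termination criterion: "When 3 of the subjects receiving apixaban experience an unprovoked major bleed", with cases involving a disqualifying protocol violation set aside.

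**The concern.** A test whose null hypothesis is equality can give evidence of a difference. Failing to reject gives no evidence of similarity, least of all when few events are expected. Hypothesis #2 asserts similarity, and the plan supplies no instrument that could show it: no margin, no tolerable upper limit, no sentence saying which feature of the intervals would count as similar.

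Major bleeding is the primary safety outcome and the foreseeable risk the protocol names for the drug. If the report sets a non-significant p-value beside a hypothesis of similarity, readers may take the hypothesis as supported when the data are compatible with a several-fold excess.

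**Working it through.** **Inputs.** 300 per arm, 1:1, two-sided 0.05 (protocol, Statistical Methods). The documents give no major-bleeding rate for placebo or apixaban. The only arm-level rates are those of the cited rivaroxaban-versus-aspirin trial in the protocol's Introduction: 0.5% (rivaroxaban 20 mg), 0.4% (10 mg) and 0.3% (aspirin). I take 0.3% as a low assumed placebo rate and 1% as a high one. Both are assumptions.

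**The plan's own figure.** For efficacy, n per arm = [1.96·√(2p̄q̄) + 0.8416·√(p₁q₁ + p₂q₂)]² / (p₁ − p₂)². With p₁ = 0.06, p₂ = 0.015 and p̄ = 0.0375, this is (0.5266 + 0.2245)² / 0.002025 = 278.6, so 279, with power 0.8005. That matches the protocol, which therefore used the uncorrected test. No corresponding figure for bleeding exists to reproduce.

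**Expected events.** 300 × 0.003 = 0.9 placebo bleeds; 300 × 0.01 = 3.

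**Power of the difference test.** Sum, over all pairs of bleed counts (a, b), the product of the two binomial probabilities wherever p < 0.05. The single-stratum Mantel-Haenszel statistic is (a − m/2)² / V, with m = a + b and V = ¼·m·(600 − m)/599.

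| Placebo rate (assumed) | True ratio | Mantel-Haenszel | Fisher |
|---|---|---|---|
| 0.3% | 2 | 4.7% | 0.4% |
| 0.3% | 3 | 12.5% | 2.5% |
| 0.3% | 4 | 22.6% | 7.4% |
| 1% | 2 | 15.8% | 9.0% |
| 1% | 3 | 42.4% | 30.6% |
| 1% | 4 | 69.1% | 58.0% |

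By the sample-size formula above, 80% power would need 7,813 per arm for 0.3% vs 0.6%, 2,600 for 0.3% vs 0.9%, and 2,319 for 1% vs 2%.

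**What single results would show.**
- 3 vs 0 bleeds: m = 3, V = ¼·3·597/599 = 0.7475, statistic 1.5²/0.7475 = 3.01, p = 0.083 (Fisher 0.25).
- 4 vs 0 bleeds: V = 0.995, statistic 4/0.995 = 4.02, p = 0.045. This is the smallest split that reaches significance. Fisher needs 6 vs 0 (p = 0.030).
- 1 vs 1 bleeds: the Wilson interval for 1/300 is 0.06% to 1.86%. The Newcombe interval for the risk difference is 0 ± √(0.27² + 1.53²) = ±1.55 points. The risk ratio interval is exp(±1.96·√(2 − 2/300)) = 0.06 to 15.9.
- 3 vs 1 bleeds: p = 0.32, with a risk-difference interval of -1.0 to +2.6 points.

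**The case against.** The strongest reply is that most of the remedy is already planned. The protocol asks for the risk difference with a 95% confidence interval, and the SAP tabulates hazard ratios with intervals for major bleeding in every analysis set. Aim #2 says only that the arms will be compared, in both documents, and the SAP omits the similarity hypothesis. This stands: it would be wrong to say that the plan offers nothing but a difference test. What is missing is any link from those intervals to the claim.

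A reader might infer that the sponsor intends to call a non-significant result safe, or that the trial would confirm Hypothesis #2 even if bleeding quadrupled. The documents do not state such a rule, and power for a quadrupling reaches 69% at the higher assumed rate. The stopping rule could also intervene. From a 0.3% base, the chance of at least 3 apixaban bleeds in 300 patients is 51% for a tripling and 70% for a quadrupling. These are upper bounds for triggering the rule, since only unprovoked bleeds without a disqualifying protocol violation count. The weaker statement survives: the similarity hypothesis and the stated purpose invite the reading, and nothing in the plan guards against it.

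A reader might also infer that the 3-bleed rule caps the evidence below significance. It does not do so strictly. Provoked bleeds and protocol-violation cases are not counted, so total major bleeds can exceed three. SAP section 6.7 describes an investigation and subsequent measures where the protocol describes termination. The power figures above assume no such cap.

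Finally, 0.3% is an aspirin-arm rate from another trial, which is why a range is shown.

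**Conclusion.** The concern holds in this form: the stated test cannot support the stated safety hypothesis, and a non-significant result is likely even with a real excess. Across assumed placebo rates of 0.3% to 1%, with all 300 per arm analysed, power is 5-16%, 12-42% and 23-69% for a doubling, tripling and quadrupling (Fisher 0.4-9%, 2.5-31% and 7-58%). The exact size depends on a rate the documents do not give. The logical gap does not: at every rate in this range the difference test has less than half the usual 80% power for a doubling and about half of it or less for a tripling, and no criterion for similarity exists at any rate. The figures use the protocol's uncorrected Mantel-Haenszel test; the SAP's log-rank test was not enumerated separately.

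This should be corrected because it governs what the trial may claim about its primary safety outcome. It is not a defect in the data to be collected, nor evidence that the sponsor plans to misreport.

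**What to change.** Reword Hypothesis #2 as estimation, consistent with the comparison wording of Aim #2 in both documents. Make the planned risk difference and hazard ratio, each with a 95% confidence interval, the main safety result. Use an exact or score interval for the risk difference because events will be few. State in the SAP that a non-significant p-value will not be described as similar or safe, and that the report will give the largest excess the upper confidence limit does not exclude. No margin is then needed.

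The cost is wording in the aims and the SAP, with no extra patients or data. The real price is a less favourable safety claim: with one bleed per arm, the report would have to say that an excess of about 1.6 points was not excluded.

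Separately, the protocol's Safety Stopping Rules (termination) and SAP section 6.7 (investigation, adjudication and measures) describe the 3-bleed rule differently and must be reconciled.
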